This study protocol is planned as parallel arm, double blind, single-centered and randomized controlled clinical trial. The ethics committee approval required for this study was obtained from Republic of Turkey, Ministry of Health, Turkish Medicines and Medical Devices Agency (21-AKD-186). The participants of the study were informed about the study protocol, benefits, possible complications and participants' human rights and an informed consent form was signed. The participants were selected from among the patients who applied to the Cukurova University, Faculty of Dentistry, Endodontic Clinic, between the dates from January to March 2022.

Sample size determination were performed according to the results of the study conducted by Lin et al. It was calculated by taking into account under the assumption that the difference is 45%, the power is 80%, and the error rate is 5%, there should be 22 patients per group. The sample size was set to 25 patients per group for possible dropouts. For randomization, the block permutation method with a computer-aided block size of 10 was used.

A total of fifty patient with the diagnosis of symptomatic irreversible pulpitis in the mandibular first or second molar teeth were include this study. The following inclusion criteria were taken as a basis; systemically healthy patients (American Society of Anesthesiologists [ASA] Class I or II) and patients between the ages of 18-65. The patients were excluded from the study if there was a pregnancy or nursery; allergy or sensitivity history against to articaine, epinephrine or any other used medication/materials; taking any analgesic drug or medication that interfere pain response 12 h before treatment. Also, patients with pathologic periodontal pockets during probing, have any pathology in the areas that planned for injection and have periapical pathology were excluded when considering clinical diagnosis.

The history of intermittent or spontaneous pain, even after the thermal stimuli have been removed, were based on the diagnosis of SIP and supported by clinical and radiological evaluation. Patients who have teeth with deep dentin caries or restored with composite/amalgam were included to the study. Teeth with crown restorations or abutments were excluded. After determining the vitality of the pulp with positive response to electrical pulp testing (Parkell Inc. NY, USA), cold testing (Endo-Frost, Coltene-Roeko, Langenau,

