Germany) were used to scale felt pain as “before the beginning of the treatment”. In radiological evaluation, it has been looked for evidence of caries or initial restoration and no change in periodontium.

In order to categorize patients' pain, the “Heft–Parker Visual Analogue Scale” (HP-VAS) was used (1) before the beginning of the treatment, (2) the beginning of the treatment, (3) after the perforation of the pulp, (4) during the extirpation of the pulp/instrumentation. HP-VAS is a 170 mm line without a value that written “no pain” in the head and “greatest pain I have ever experienced” at the end. This line was measured and divided into 4 categories; 0=no pain, ≤54 mm mild pain, 54-114 mm moderate pain, ≥114 mm severe pain.

Blinding and anesthesia procedures

The fifty patients that included in the study were randomly divided into 2 groups (n=25) in accordance with the randomization block. All anesthetic attempts were performed by an endodontist ([name]) who received the patients according to the group and teeth were isolated with rubber-dam to maintain the blindness. In all applications, 4% articaine hydrochloride with 1:100.000 epinephrine (Ultracaine® DS Forte ampule and cartridge, Sanofi Aventis, Germany) was used as anesthetic solution.

IANB group: A standard IANB injection was performed with a standard 27-G needle and dental injectors (Septodont, Saint-Maur-des-Fosses Cedex, France) using the traditional Halsted approach. After determining the injection site and performing aspiration, 1.8 mL of solution was injected at a rate of 1 mL/min to block the inferior alveolar nerve. The patient was questioned about lip numbness after fifteen minutes. If there was no numbness, patient was excluded. In the case of lip numbness was achieved, 1 mL of buccal infiltration anesthesia was applied to the buccal sulcus of the tooth. Then, tooth was isolated with rubber dam.

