ILI group: Initially, 1 mL of buccal infiltration anesthesia was administered to the buccal sulcus of the tooth with a standard 27-G needle and dental injectors. After five minutes, ILI was performed using an ILI device (Sopira Citoject, Heraeus Kulzer GmbH Hanau, Germany) with needle of 30-G and 12 mm in length (Sopira Carpule). The needle tip was held obliquely to the long axis of the tooth and slowly entered to the periodontal ligament until feeling constant and uninterrupted back pressure. It was ensured that the needle was correctly placed in the periodontal area. Anesthetic solution was injected at 4 location (mesiobuccal, distobuccal,

mesiolingual and distolingual) in each tooth. Sophira device administers 0,06 mL anesthetic solution in each dosing unit. Thus, it was triggered 3 times for each location (0,18 mL) to achieve subsequent anesthesia. Totally, 0,72 mL solution were injected for each tooth. Then, tooth was isolated with rubber dam.

Endodontic intervention

Access cavity preparation was performed using a round bur by an endodontist ([name]) who is blinded about the participants' group. When the patient felt pain, the intervention was stopped and patient was allowed to mark on the HP-VAS. If the patient did not feel pain until the perforation of pulp chamber, it was recorded as no pain. After the perforation of pulp chamber, pulp was removed using a sharp excavator and HP-VAS was marked thirdly. Then, root canals were established using a size 10 K-file and working lengths were determined using an electronic apex locator. All root canals were prepared with Reciproc® (VDW, Munich, Germany) using an endomotor (VDW Gold; VDW, Munich, Germany). HP-VAS was marked again by patient to assign the felt pain during instrumentation. If this marking was no pain to mild pain, then the anesthesia was recorded as "successful". If this marking was moderate pain to severe pain, then the anesthesia was recorded as "failed". In the existence of pain, additional injections were administered in every stages of treatment belongs to intervention group (IANB or ILI or intrapulpal if pulpal perforation occurs). Root canal treatment was completed with routine irrigation and obturation procedures in a single visit.

Statistical Analysis

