IBM SPSS Statistics Version 20.0 package program was used for statistical analysis of the data. Categorical measurements were summarized as numbers and percentages, and numerical measurements were summarized as mean and standard deviation. Chi-square test statistics were used to compare categorical measures between groups. The ShapiroWilk test was used to determine the assumption of normal distribution of the numerical measurements. Independent T test was used to compare the mean age of the groups. Generalized EstimatingEquations (GEE) method was used to examine the change in HP-VAS values during intervention and to determine the features that affect this change. Statistical significance level was taken as 0.05 in all tests.

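### The GEE on HP-VAS, with at most 25 patients per arm, states no small-sample correction and no role for the pre-treatment mark; uncorrected robust tests would run at about 6–8.5%, not 5%

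*Combined protocol and SAP*

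**What the plan says.** The Statistical Analysis section states what the GEE is for (the "method was used to examine the change in HP-VAS values during intervention and to determine the features that affect this change") and sets one threshold: "Statistical significance level was taken as 0.05 in all tests". It names SPSS 20.0 but gives no GEE options: no link, working correlation, covariance estimator, test statistic or covariate list.

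Materials and Methods lists four HP-VAS occasions, starting with "1) before the beginning of the treatment, (2) the beginning of the treatment" and followed by marks after pulp perforation and during extirpation or instrumentation. The first mark comes from cold testing, whose results "were used to scale felt pain as" the pre-treatment value. No section says whether that mark is an outcome level in the GEE, a covariate, or unused.

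On numbers: "The fifty patients that included in the study were randomly divided into 2 groups (n=25" each). The IANB group paragraph adds, on lip numbness, "If there was no numbness, patient was excluded", so that arm may be smaller; by how many is not given. Under Endodontic intervention, "If the patient did not feel pain until the perforation of pulp chamber, it was recorded as no pain", so exact zeros may be frequent.

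**The concern.** A robust (sandwich) variance estimated from few clusters is biased downward, and a chi-square reference ignores its sampling error. Both make p-values too small. Here the clusters are patients, 50 at most. The plan applies 0.05 to every test, so an ordinary large-sample GEE run under this text would not hold the level that the text claims.

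The open role of the pre-treatment mark adds to this. As a fourth outcome level it makes the group × stage test a 3-df test, which is inflated more than the 2-df test on three marks.

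At stake is a borderline HP-VAS result. A group or group × stage effect could be called significant when an accurate reference would not support it.

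**Working it through.** **The plan's own figure.** The sample size rests on "the difference is 45%, the power is 80%, and the error rate is 5" per cent; the two rates are not stated. The continuity-corrected two-proportion formula, two-sided, is

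n₀ = [1.960·√(2p̄(1−p̄)) + 0.842·√(p₁(1−p₁)+p₂(1−p₂))]² / d², n = (n₀/4)·[1+√(1+4/(n₀d))]².

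With d = 0.45 and assumed rates 0.20 and 0.65, n₀ = 17.7 and n = 21.9, so 22. Lower rates from 0.15 to 0.40 give 22 or 23. The stated 22 reproduces. It concerns the success proportion and has no bearing on the GEE.

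**Exact level of the uncorrected robust test.** Take n per arm, an identity link and a saturated arm × stage model. The robust variance is then (n−1)/n times the unbiased one. With ν = 2n−2, the level of a q-df chi-square test is

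P{ F(q, ν−q+1) > χ²_q(0.95) · ((n−1)/n) · (ν−q+1)/(νq) }.

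For n = 25:
- q = 1: 3.8415 × 0.96 = 3.688 on F(1,48), giving 6.08%.
- q = 2: 5.9915 × 0.96 × 47/(48×2) = 2.816 on F(2,47), giving 7.00%.
- q = 3: 7.8147 × 0.96 × 46/(48×3) = 2.397 on F(3,46), giving 8.03%.

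| Test | 25 per arm | 22 per arm |
|---|---|---|
| Group contrast, 1 df | 6.1% | 6.2% |
| Group × stage, 3 marks, 2 df | 7.0% | 7.3% |
| Group × stage, 4 marks, 3 df | 8.0% | 8.5% |

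Under normality with equal arms and equal covariance, these need no assumed SD, correlation or mean profile. An F reference on the uncorrected variance is only a partial repair: 5.5% (1 df) and 5.9% (2 df) at 25 per arm.

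**Simulation away from those conditions.** Three marks, baseline covariate, exchangeable working correlation; arms 25/25, 22/25 and 18/25 (the smaller IANB sizes are assumptions); normal scores, scores clipped to 0–170, and scores with 38–46% zeros. Fifteen cases of 20,000–40,000 runs each, Monte Carlo error 0.1–0.2 points.

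| Method | Group, 1 df | Group × stage, 2 df |
|---|---|---|
| Robust, chi-square | 6.2–6.8% | 6.7–7.4% |
| Robust, F | 5.5–6.0% | 5.5–6.2% |
| Kauermann-Carroll, F | 4.8–5.2% | 4.8–5.5% |
| Mancl-DeRouen, F | 4.1–4.4% | 4.2–4.9% |
| Model-based covariance | 5.5–5.9% | 5.0–5.6% |

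The model-based row has the working correlation correct by construction.

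**Feature tests.** In a separate simulation of the uncorrected robust test at 22–25 per arm, a binary feature was tested at 6.5–7.6%, and the group test with two added binary features ran at 6.5–8.0%. Continuous features, with three covariates and an independence working correlation, ran at roughly 8–9%. A Mancl-DeRouen-type variance still referred to chi-square left the 2-df test at about 5.2–6.2% and the 3-df test at 6.1–6.9%, so the F reference is needed as well.

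**Value of the pre-treatment mark.** The net reduction in the standard error of the stage-averaged group difference is 1 − √(1−r²/v)·√(1+1/46), with v = (1+2ρ)/3, where ρ is the correlation between marks and r that between baseline and later marks. The factor 1+1/46 is the cost of one slope. For ρ = 0.3 and 0.5: −0.1% and −0.3% at r = 0.1; 2.8% and 2.0% at r = 0.2; 7.8% and 6.0% at r = 0.3. The documents give neither r nor ρ.

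**The case against.** The strongest reply is that no error has been shown. The estimator is not named, and with a model-based covariance and a suitable working correlation the excess is under one point. That stands: a reader might infer that the trial's HP-VAS p-values are inflated, and the documents do not support it. They support only that the plan leaves open a common choice that would inflate them.

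The effect is also small, and it falls on a supporting analysis. That stands too. A reader might infer that the success comparison or the sample size is undermined; neither uses the GEE.

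Third, baseline adjustment can be called a preference. A reader might infer that leaving the pre-treatment mark out biases the comparison. In a randomised trial it does not, and nothing in the documents shows that pain on cold testing predicts intra-operative pain. What remains is that the role must be stated, because it decides whether the interaction has 2 or 3 df.

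Finally, a remedy limited to group, stage and baseline would miss the plan's second purpose, finding features that affect the change. That is right, so the fix below covers those tests.

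**Conclusion.** The point holds as a minor one. The plan tests HP-VAS at 0.05 on 50 patients or fewer without saying how the small-sample behaviour of GEE is handled. Conditional on uncorrected robust chi-square tests, the excess is one to two points for the group contrast, about two to two and a half for the 2-df interaction, and three to three and a half for a 3-df interaction with four outcome levels. At 25 per arm, a reported p of 0.050 then corresponds to about 0.061 (1 df) or 0.070 (2 df).

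The exact figures rest on normal scores, equal arms and equal covariance. The simulations show similar levels with bounded scores, many zeros and unequal arms. Correlations, score distributions and IANB losses are assumed. The corrected methods were not simulated for the feature tests themselves.

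**What to change.** State in the Statistical Analysis section:

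- **Model.** GEE on the three intra-operative marks, with patient as cluster, group, stage and group × stage, and the pre-treatment HP-VAS as a covariate.
- **Inference.** A bias-corrected sandwich variance (Kauermann-Carroll, or the slightly conservative Mancl-DeRouen) with a t or F reference; or a mixed model with small-sample degrees of freedom. An F reference on the uncorrected variance is not enough.
- **Features.** List them, and apply the same correction to each. Use df equal to patients minus the number of patient-level parameters in that model: with 50 patients, 47 for intercept, group and baseline, and one fewer for each feature parameter added.
- **Reporting.** Give the group difference with a 95% CI at each stage, including the instrumentation mark that defines success, as well as any average over stages. Note that later marks may follow additional injections.
- **Fallback.** The documents do not show whether SPSS 20.0 offers these corrections. If it does not, use ANCOVA on each patient's mean of the three marks, adding any feature as a covariate (simulated level for the group test with baseline only, 4.7–5.1%), and a two-group multivariate F test on the between-stage differences (4.4–5.2%).

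If the analysis has already been run, report which estimator and reference were used.

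**Cost.** SAP wording, one degree of freedom for baseline, possibly another procedure, and no new data. For 1–2 df tests at 22–25 per arm, without a covariate and on patients minus 3 df, an uncorrected p of 0.050 becomes 0.061–0.069 with Kauermann-Carroll and 0.066–0.077 with Mancl-DeRouen. If r is only about 0.1, baseline adjustment gains nothing.
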